12.5 Secondary Endpoint(s)

12.5.1 Is the number of impaired neuropsychological tests in the COGNUTRIN supplementation group mediated by changes in cytokines and anti-oxidant markers? In order to examine the mediation of the intervention group effects on number of impaired neuropsychological tests by changes in biomarkers, we will adopt a bootstrapping approach to this analysis. Baron and Kenny's approach to regression-based statistical mediation. In this case, the 95% confidence intervals around the bootstrapped indirect estimate will be examined to evaluate whether the mediation relationship is statistically significant. Again, the analyses here are focused on generating information regarding the size of the effects, rather than statistical significance.

12.5.2 We thus propose to evaluate both chemotherapy-induced changes in structural and functional parameters by evaluating (a) differences in cerebral white matter integrity [fractional anisotropy (FA) and mean diffusivity (MD)] maps before and after treatment with COGNUTRIN by using magnetic resonance DTI; (b) we will perform resting state fMRI to determine changes in the connectome in breast cancer patients treated from baseline and post intervention with COGNUTRIN compared to placebo. To date, imaging studies have only focused on assessing structural and functional cognitive disruption induced by chemotherapy. The proposed study aims to replicate these findings and extend them by testing the proposed interventions ability to offset the changes in cognitive performance in breast cancer patients post chemotherapy treatment.

12.5.3 Evaluate the effects of COGNUTRIN on changes in subjective cognitive function. We will evaluate the effect of COGNUTRIN on changes in subjective cognitive function; Compliance will be evaluated by standard pill counts, diet records and plasma levels of anthocyanins and erythrocyte n-3 index. Any unusual patterns in compliance will be noted and apparent discrepancies between pill counts or diet records and plasma levels will be summarized as well. The collected data will be entered through screens created by the Research IT analyst in ONCORE, the Research Data Management Systems used at the MCC.

12.5.4 Evaluate the effects of COGNUTRIN on changes in symptoms of fatigue and depression. Additionally, we will evaluate the effect of COGNUTRIN on changes in symptoms of fatigue and depression. Medication use such as antidepressants, tranquilizers and anxiolytics will also be obtained at baseline and

throughout the study. As with age and fatigue, we will evaluate the effect of these medications for association with neurocognitive performance and entered as covariates in statistical analyses if a marginally significant association ($p < .10$) is observed.

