shown to cross the blood brain barrier and localize in various brain regions important for learning and memory such as cerebellum, striatum and hippocampus in measurable quantities. Studies have correlated peripheral markers of inflammation, immune function and oxidative stress in serum/plasma with central inflammation and central nervous system functioning. Thus based on the etiologies of cognitive changes, animal and early clinical trial evidence of safety, bioavailability in blood and brain tissue and preliminary evidence of efficacy to improve CF, it is logical to test the effectiveness of a combination standard nutrition supplement that can provide anti-oxidant, anti-inflammatory nutrients critical to the physiochemical composition and functioning of the neurological system to “rescue” tissues from the effects of the oxidative damage and inflammation and reverse chemotherapy-induced cognitive impairment as we propose in this study.

1.6 Structural and functional imaging markers of cognitive function: Self-reported poor concentration or ‘chemo-brain’ has been validated using neuropsychological tasks and more recently, neuroimaging studies have identified structural¹²³ and performance differences between patients (i.e. those treated with chemotherapy) and controls^{122,124,126}. For example, a recent functional Magnetic Resonance Imaging (fMRI) study has demonstrated that when compared to controls, chemotherapy treated patients show hyporesponsiveness in areas of the brain associated with impaired planning behavior and attentional abilities (i.e. parahippocampal gyrus, left cuneus, right dorsal striatum, right inferior parietal cortex and left middle temporal gyrus). What is more, functional imaging studies have shown these disruptions last from one month following treatment¹²⁶ to 10 years following treatment.¹²²

To date, imaging studies have only focused on assessing cognitive disruption induced by chemotherapy. The proposed study aims to replicate these findings and extend them by testing the proposed interventions (e.g. COGNUTRIN®) ability to offset the changes in cognitive performance in breast cancer survivors post chemotherapy treatment.

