4.1 Inclusion Criteria. 1) Women 30-70 years of age 2) Cases with Stage I-IIIB Breast Cancer that have completed neoadjuvant or adjuvant treatment with anthracyclines and/or taxanes + or –Radiation therapy within past 6 months (+/- 7 days) (subjects on concurrent endocrine therapy (TAM, Aromatase inhibitors are also eligible to participate as this is standard of care for this patient population) 3) Able to understand and sign the informed consent. 4) Fluent in reading, comprehension and communication in the English language. (Persons who are unable to meet this requirement are excluded from the current proposal because many of the cognitive tests that are administered are in English and translation of these instruments in other languages is currently unavailable) 5) No evidence of dementia (MMSE \geq 23) but some evidence of cognitive impairment (each subject will be required to answer in the affirmative: ‘do you have problems with memory and attention since having chemotherapy, and do you believe chemotherapy contributed to the problems?’); 6) Each subject must be aware of the nature of his current medical condition and must be willing to give consent after being informed of the experimental nature of therapy, alternatives, potential benefits, side-effects, risks and discomforts. 7) ECOG performance status of 0- 2 (8) Acceptable hemoglobin and hematocrit level based on CBC. (9) All subjects must be willing to be monitored for adequacy of nutritional intake during the intervention, as is the current standard of clinical practice.

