6.1 Dose Regimen and Dose Groups: Intervention groups

6.1.1 Placebo Group: All participants in the placebo arm will receive the multivitamin supplement and the cognitive battery tests and structural and resting-state functional imaging at baseline and 3 months. The placebo group used herein will allow us to generate information regarding the reliable change index, so information regarding the naturalistic change in cognitive performance, as well as the potential for practice effects to influence mean-level change data, across the follow-up period is important.

6.1.2 Nutritional Supplement Group (NS): The choice of the supplement to use in this trial is based on relevant research supporting the various components as well as the use of a commercially available standardized dietary supplement of anthocyanins and n-3 fatty acids. The supplement to be used is a standardized formulation of blueberry extract VitaBlue® (40% polyphenolics, 12.5% anthocyanins from blueberries. The supplement will in addition include Lovaza® (omega-3-acid ethyl esters), an FDA-approved prescription omega-3 provides prescription-only potency and purity with each 1-gram Lovaza® (omega-3-acid ethyl esters) gel capsule contains 90% omega-3-acid ethyl esters; 84% eicosapentaenoic acid (EPA) and docosahexaenoic acid (DHA) ethyl esters. Lovaza® is provided by GlaxoSmithKline, who has authorized the FDA center for Drug Evaluation and Research, Division of Metabolic and Endocrine Drug Products to reference Lovaza® Capsules IND # 45,998. An investigator-initiated IND has been obtained by PI for use of these agents in this clinical trial (IND # 116424). Subjects in the supplements treatment arm of the study will be given in the same fashion and time table to the "placebo" patients as the active treatment patients.

6.2 Agent Administration: Intervention will be administered to the patient on an outpatient basis and self-administered by the participants. The daily dose of will be taken in divided doses (Lovaza® 2 tablet BID and Vitablue™ 2 tablet TID). On the day of monthly follow-up visit, capsules should be taken within 4 hours of visit and blood draw for required lab work.

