7.3 Evaluations during Baseline/Randomization Visit

7.3.1 After eligibility has been confirmed based on screening tests using eligibility checklist, subjects will be randomized and supplied with a one-month supply of nutritional supplement (COGNUTRIN) or placebo (n=20/arm) and multivitamin .

7.3.2 Review of completed diet survey and concomitant medications.

7.3.3 Anthropometric measurements will be taken.

- 7.3.4 The following questionnaires will be completed: Godin-Leisure Time Exercise, Patient's Assessment of Own Functioning Inventory (PAOFI); Personal Health Questionnaire (PHQ-9), and Symptoms of Fatigue and Depression (FSI)
- 7.3.5 Cognitive testing will be administered (HVLТ-R: Form 1, COWA: T1, Color Trails Part 1& 2, Digit Span, SDMT, BVMT-R: Form 1, and Rey Complex Figure Copy)
- 7.3.6 Subjects will also undergo a structural and resting-state functional magnetic resonance Imaging (MRI/fMRI)

Subjects should not be randomized until eligibility has been confirmed. All components of eligibility will be confirmed (inclusion criteria and exclusion criteria).

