Compared to healthy females, the breast cancer group displayed altered global brain network organization characterized by significantly decreased global clustering as well as disrupted regional network characteristics in frontal, striatal and temporal areas. Breast cancer survivors also showed significantly increased self-report of executive function and memory difficulties compared to healthy females. These results suggest that topological organization of both global and regional brain network properties may be disrupted following breast cancer and chemotherapy. This pattern of altered network organization is believed to result in reduced efficiency of parallel information transfer. This is the first report of alterations in large-scale functional brain networks in this population and contributes novel information regarding the neurobiologic mechanisms underlying breast cancer-related cognitive impairment¹⁵³⁻¹⁵⁴.

We thus propose to evaluate both chemotherapy-induced changes in structural and functional parameters by evaluating (a) differences in cerebral white matter integrity [fractional anisotropy (FA) and mean diffusivity (MD)] maps before and after treatment with COGNUTRIN by using magnetic resonance DTI; (b) we will perform resting state fMRI to determine changes in prefrontal executive functioning in breast cancer patients treated from baseline and post intervention with COGNUTRIN compared to placebo. To date, imaging studies have only focused on assessing structural and functional cognitive disruption induced by chemotherapy. The proposed study aims to replicate these findings and extend them by testing the proposed interventions ability to offset the changes in cognitive performance in breast cancer patients post chemotherapy treatment.

Subjects will be provided prepared, specific and consistent instructions over the intercom prior to start of MRI as follows: “Keep your eyes closed, relax, try not to move, try to stay awake and just let your thoughts wander.” All subjects will be imaged on a 3T scanner with an eight channel phased- array head coil. **Time in scanner for technician getting the imaging optimized for the patient is 5 minutes.**

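### The imaging sections promise to evaluate chemotherapy-induced change, which two post-chemotherapy scans cannot show, and they name two different resting-fMRI targets without fixing a measure for either

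*Combined protocol and SAP*

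**What the plan says.** **The task.** Section 12.5.2 opens: "We thus propose to evaluate both chemotherapy-induced changes in structural and functional parameters". Section 7.7.14 has the same sentence. Sections 1.6, 7.7.14 and 12.5.2 each add: "The proposed study aims to replicate these findings and extend them". The findings described in 1.6 and 7.7.14 compare chemotherapy-treated patients with controls or healthy women.

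**The design.** Inclusion criterion 2 in section 4.1 admits cases "that have completed neoadjuvant or adjuvant treatment with anthracyclines and/or taxanes". Section 6.1.1 gives the placebo arm "structural and resting-state functional imaging at baseline and 3 months", and Table 1 in section 7.1 shows the same two imaging times for all participants. The only arms are COGNUTRIN and placebo, 20 each (section 7.3.1).

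**The resting-fMRI target.** Section 7.7.14: "we will perform resting state fMRI to determine changes in prefrontal executive functioning in breast cancer patients". Section 12.5.2, in an otherwise almost identical sentence: "we will perform resting state fMRI to determine changes in the connectome in breast cancer patients". Both are current text.

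**The DTI item.** Item (a) in both sections names fractional anisotropy (FA) and mean diffusivity (MD) maps, compared before and after COGNUTRIN. Placebo appears only in item (b), on resting fMRI.

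**The randomised contrast.** The schema lists, as a secondary endpoint, structural and resting-state changes after 3 months on COGNUTRIN versus placebo. Specific Aim 3 asks about supplementation relative to no supplementation. Section 8.2 repeats the imaging endpoint without naming a measure.

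**The concern.** Two things in the imaging text do not fit the trial.

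First, evaluating chemotherapy-induced change needs a pre-chemotherapy scan or an unexposed comparison group, and this trial has neither. If the sentence stays in the statistical section, a 3-month change could be reported as chemotherapy damage being offset. The data could not show that the baseline value was abnormal, or that chemotherapy caused it.

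Second, section 3.0 lists effect-size estimation among the products of the pilot, and section 8.2 says effect sizes will motivate future trials. An effect size belongs to a named variable. With two labels and no metric, the fMRI value carried into the next trial's planning could be picked from many candidates once results are known, and a value picked for its size tends to overstate the effect.

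**Working it through.** The documents give no sample size, power or effect size for imaging, so there is no figure to reproduce. The check is of what the design identifies and what the text fixes.

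**1. What two post-chemotherapy scans can estimate.** For any imaging measure, let m be the mean these women would have had without chemotherapy, C the chemotherapy effect present at baseline, n the change over 3 months without the supplement, and s the supplement effect.

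| | Baseline | 3 months | Change |
|---|---|---|---|
| Placebo | m + C | m + C + n | n |
| COGNUTRIN | m + C | m + C + n + s | n + s |

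- Difference in change between arms: (n + s) − n = s. Randomisation identifies this.
- C appears only inside the sum m + C. Nothing in the trial observes m, so C cannot be separated.
- The placebo change n is not C either. It mixes any recovery or progression with concurrent endocrine therapy and recent radiation (both allowed by section 4.1) and with scan-to-scan variation.
- DTI item (a), read literally, estimates n + s. Subtracting the placebo change is what isolates s.

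The only non-cancer reference is the CA- sample in section 7.7.9. It standardises cognitive scores, and no section has it scanned.

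**2. What the fMRI text fixes.**

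| Section | Target | Metric |
|---|---|---|
| Schema, 8.2 | Resting-state changes | None |
| Specific Aim 3 | Resting-state functional markers | None |
| 7.7.14 | Prefrontal executive functioning | None |
| 12.5.2 | The connectome | None |

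Section 7.7.14 itself describes resting networks as independent of task. Section 7.7.9 assigns executive functioning to Color Trails Part 2 and the Symbol Digit Modalities Test. The 7.7.14 target is therefore a cognitive domain measured elsewhere in the battery. A connectome can be summarised in many ways, and none is chosen. Section 12.4 names a repeated measures ANOVA for neuropsychological outcomes and 12.5.1 a bootstrap for mediation, but 12.5.2 names no model for imaging.

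**3. Precision of one imaging effect size.** For a between-arm difference in mean change, in units of the SD of change, the 95% CI half-width is t(0.975, 2n − 2) × √(2/n), with n here the number per arm.

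- 20 per arm: 2.024 × √(2/20) = 2.024 × 0.3162 = 0.64 SD.
- 18 per arm, if 40 are randomised and the 10% loss in section 4.3 occurs (20 × 0.9 = 18): 2.032 × √(2/18) = 2.032 × 0.3333 = 0.68 SD.

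The difference detectable with 80% power at two-sided 5% (noncentral t) is 0.91 SD at 20 per arm and 0.96 SD at 18. An estimate this imprecise has wide room for selection if the measure is not fixed first. The amount of selection cannot be calculated, because the plan does not say how many measures would be examined.

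**The case against.** The strongest reply is that the chemotherapy wording is loose rationale and not a planned analysis. In 12.5.2 the sentence goes on to items (a) and (b), both of which evaluate COGNUTRIN. The replication sentence goes on to testing whether the intervention can offset the changes. Section 1.6 is background. Much of this stands: no chemotherapy test is planned, and that such results would be misreported is a risk, not a stated intention. But the sentence sits in the statistical section as what will be evaluated. The charitable reading, reversal of chemotherapy damage, still needs evidence that the baseline is abnormal because of chemotherapy. Reference 124 in the protocol's own list concerns, by its title, differences between patients and controls before chemotherapy.

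On fMRI, section 7.7.14 links the connectome to graph theoretical analysis and reports both "significantly decreased global clustering" and regional differences, including frontal ones. A frontal target could therefore be a regional part of a connectome analysis, and the two labels need not be rivals. That is a fair point about framework, but it does not select a measure.

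A reader might go further and infer that the imaging aim has no answer at all. The documents do not support this. The schema, Specific Aim 3 and item (b) of 12.5.2 state the randomised comparison, and FA and MD are named consistently. The schema's contrast with placebo also covers structural imaging, so the DTI gap is one of wording in item (a). A reader might also want to count false positives across every brain connection. The plan contains no atlas and no connection-by-connection test, so such a count would not describe this trial.

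Finally, this is a secondary endpoint in a pilot that says it lacks power. That limits the importance of the point, but estimation also needs a defined variable.

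**Conclusion.** The concern holds in limited form. The plan states a task its design cannot perform: the chemotherapy effect is not identified by any contrast in the trial. It gives two different resting-fMRI targets, neither reduced to a measurable quantity, and it writes the DTI comparison without placebo. The randomised estimate of the supplement effect on imaging is unaffected by the first problem and can be obtained once a measure is fixed, with a 95% CI of about ±0.64 SD of change at 20 per arm.

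The identification argument rests only on the eligibility criteria, the scan times and the absence of a scanned unexposed group. The precision figures assume a two-sample comparison of change scores with equal variances and normality. The sponsor should correct the text. The importance is moderate, because the endpoint is secondary and the trial is a feasibility pilot.

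**What to change.** 1. In 1.6, 7.7.14 and 12.5.2, delete the claims to evaluate or replicate chemotherapy-induced change. State that all imaging results, DTI and resting fMRI alike, will be interpreted only as between-arm differences in 3-month change.
2. Use one resting-fMRI measure in 7.7.14, 8.2 and 12.5.2, fixed before unblinding. Change in global clustering coefficient is a suitable example, since the rationale in 7.7.14 reports it as reduced in chemotherapy-treated survivors. The documents do not show that it responds to a supplement, and another single measure would also serve.
3. Add the comparison with placebo to DTI item (a) in both sections. Report each named imaging measure as a between-arm difference in change with a 95% CI.
4. Label regional and connection-level results exploratory.

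The cost is protocol wording only. Scans, visits and sample size stay the same. The downside is that regional findings lose endpoint status.

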12.6 Evaluation of Toxicity

The primary safety endpoint is incidence and severity of AEs occurring during intervention with either COGNUTRIN or placebo. All participants will be evaluated for toxicity from the time that the informed consent is signed up to the end of the intervention according to the NCI CTCAE version 4.0. Standard assessment of toxicity will also include interviews, clinical evaluation, and monitoring of laboratory values. All toxicity data will be summarized by category and grade in a standard fashion. Proportions experiencing most common types of toxicity in this trial will be estimated and exact 95% CIs calculated based on the exact binomial distribution for these proportions will be reported. Compliance will be evaluated by standard pill counts, diet records and plasma levels of anthocyanins and erythrocyte n-3 index. Any unusual patterns in compliance will be noted and apparent discrepancies between pill counts or diet records and plasma levels by will be summarized as well.

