7.6 Post-intervention Follow-up Period (7 days +/- 3 days)

Subjects will be contacted by telephone 7 (+/-3) days after discontinuing study agent to capture any signs and symptoms occurring since stopping the study drug and changes to concomitant medications. The subject is considered off study after telephone contact is completed.

7.7 Methods for Clinical Procedures:

7.7.1 Demographic Data: At baseline, in addition to the set of intake questionnaires designed to evaluate an expanded set of demographic characteristics, self-reported health, lifestyle activity participation completed at screening, the following data will be collected at baseline (Appendix II). Data regarding menopausal status will also be obtained. (Pre-menopausal, post menopausal and CRA (Chemotherapy related amenorrhea will be defined as without menstrual periods for a period equal to or over 6 months in a patient who was premenopausal at diagnosis).

7.7.2 Anthropometric measurements such as participant's height, weight, BMI, waist and hip circumferences (Appendix III) will be obtained at baseline and at 3 months. These will be measured by a trained CRC using standardized techniques utilized and validated in our previous trials,¹⁰⁴⁻¹⁰⁵ and used to calculate body mass index (Weight kg/ Height m²) and waist: hip ratio. Our group has experience in the use of these methods in this patient population in clinical practice as well as in previous studies.

7.7.3 Physical Activity (PA) will be obtained at baseline and at 3 months using the Godin-Leisure Time Exercise Questionnaire¹⁰⁶ (Appendix IV). They will be reviewed by the study staff to monitor for increase in physical activity and to ensure that subject in not participating in strenuous activities.

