7.7.5 Functional markers (Eastern Cooperative Oncology Group: ECOG)¹¹⁰ (Appendix VI): Functional Markers allow subjects to be monitored for basic functional status and to monitor any functional impairment. Limitations in the activities of daily living have been identified secondary to fatigue and lethargy reported by this patient population. (Screening & 3 months)

7.7.6 Participants will also be provided with **Study Agent Intake and Symptom log** (Appendix VII) which they will be required to complete daily. Study agents and instructions for administration will be distributed to subjects at baseline and monthly during scheduled visits. Each batch will contain a supply for approximately 1 month. The study intake log will require the subject to check that study agent has been taken and will be secured to the symptom monitoring scale to ease completion and to remind patients to monitor symptoms.

7.7.7 Pill counts will be completed at monthly visits prior to providing subject with a new batch of supplements. Working at a flat surface, the research coordinator applies a pair of latex gloves and then pours the

bottle of study agent/placebo or multivitamin on to the pill count tray. Using a gloved hand or sorter the pills are counted individually and returned to the empty bottle. In the event of discrepancy between actual and expected count, the process is repeated.

7.7.8 Adverse events monitoring (Appendix VIII):

All adverse events (AEs) that are reported by the subject, detected during a visit, physical examination, or laboratory work-up will be recorded in the participant's study record and recorded on the CRF. All AEs that occur after the start of the study agent will be recorded on the AE CRF whether or not related to study agent. The following information will be captured for each AE: date reported; verbatim term; CTCAE Term (v 4.0); onset and resolution date; severity grade; attribution to study agent; whether or not the event was reported as an SAE; action taken; whether or not the subject dropped due to the AE; outcome; and comments.

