For each subject, AE's will be collected at the screening, Month 1, Month 2, Month 3/EOT, visits as well as at the 7-day post-treatment follow-up call by the clinical research coordinator. AE's collected at the screening visit will be catalogued as baseline symptoms by the clinical research coordinator and the AE log will be reviewed and signed by either the patient's medical oncologist or PI. AE's collected during Month 1 and 2 visits will be reviewed with the patient by the nurse who drew their blood at CRU and the AE log will be signed by the principal investigator. Finally, at the Month 3 visit, the participant's medical oncologist will review the AE log with the patient and sign-off on the reported symptoms; if the medical oncologist is unavailable to sign the AE log at this visit, then the PI will review and sign the form. AE's reported at the 7-day follow-up call will be reviewed and signed by the PI. The participant's reported symptoms at this time point will be documented on a powerchart telephone note by the clinical research coordinator. Serious adverse events (SAE's) are reported to IRB and FDA. If a participant reports an SAE, the PI will immediately be informed and she will then report it to the IRB and FDA. AE logs will be scanned to patients' medical records by the clinical research coordinator once they are off-study.

7.7.9 Assessment of Cognitive Performance.

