8.1 Primary Endpoint

The primary efficacy endpoint is to generate effect sizes for changes in the number of impaired neuropsychological tests. The planned intervention period is three months. Neuropsychological outcomes will be examined using a 2 (group; COGNUTRIN, placebo) X 2 (time; baseline, three-months) repeated measures ANOVA to examine differences in the number of impaired neuropsychological tests. Age, premorbid cognitive functioning, depression and fatigue will be evaluated for association with neurocognitive performance and entered as covariates in statistical analyses if a marginally significant association ($p < .10$) is observed.

The primary safety endpoint is incidence and severity of AEs occurring during intervention with either COGNUTRIN or placebo. All AEs that are reported by the subject, detected during a visit, physical examination, or laboratory work-up will be recorded in the participant's medical record and recorded on the CRF. All AEs that occur after the informed consent is signed will be recorded on the AE CRF whether or not related to study agent.

The sample size proposed in the current protocol will not provide sufficient statistical power, but information regarding effect sizes will be gathered and used as motivation for future clinical trials. We estimate that a minimum evidence of improvement in cognitive function with the 3 month intervention as indicated by a score of 1 standard deviation or more above population norms on the Hopkins Verbal Learning Test – Revised, Controlled Oral Word Association Test, or Color Trails Test Part 1 or 2 will be considered adequate to justify progression to a larger study.

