10.1 Adverse Events

10.1.1 Reportable AEs

All AEs that are reported by the subject, detected during a visit, physical examination, or laboratory work-up must be recorded in the participant's medical record and recorded on the CRF. All AEs that occur after the start of study agent must be recorded on the AE CRF whether or not related to study agent.

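### The adverse event window for the primary safety endpoint is set inconsistently across 7.7.8, 8.1, 10.1.1 and 12.6, and events found at the 7-day call have no stated place in the analysis

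*Combined protocol and SAP*

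**What the plan says.** **Endpoint.** Sections 8.1 and 12.6 carry the same definition: "The primary safety endpoint is incidence and severity of AEs occurring during intervention with either COGNUTRIN or placebo".

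**Evaluation window.** The next sentence of 12.6 reads: "All participants will be evaluated for toxicity from the time that the informed consent is signed up to the end of the intervention". The section then summarises all toxicity data by category and grade, with exact binomial 95% intervals for the commonest types.

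**Start of recording.** Section 8.1, under the primary safety endpoint: "All AEs that occur after the informed consent is signed will be recorded on the AE CRF". Section 10.1.1: "All AEs that occur after the start of study agent must be recorded on the AE CRF". Section 7.7.8 agrees with 10.1.1: "All AEs that occur after the start of the study agent will be recorded on the AE CRF".

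**Screening events.** Section 7.7.8 collects AEs at the screening visit and adds: "AE's collected at the screening visit will be catalogued as baseline symptoms by the clinical research coordinator". Table 1 (section 7.1) marks AEs at months 1, 2 and 3 and at the 7-day follow-up, with no mark at screening or baseline.

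**After treatment.** Section 7.6 provides a telephone contact 7 (+/-3) days after the agent is stopped, "to capture any signs and symptoms occurring since stopping the study drug". Section 7.7.8 and Table 1 both count this call as a point of AE collection.

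**The concern.** An analyst building the safety table must know which events enter the numerator. The text supports at least three answers: events during the intervention; events from consent to the end of the intervention; and everything on the AE CRF, which itself starts at two different times and has no stated end.

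The choice matters because AE incidence and severity is a primary endpoint and section 6.5 promises a formal safety comparison between arms. Events before the first dose cannot be caused by either product, so counting them adds background to both arms. Events in the days after stopping can still be related to the product. The trial makes a call to find them, and the window in 12.6 then closes before that call. With arms this small, one participant is enough to change a reported percentage visibly.

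**Working it through.** The plan states no figure for this point, so there is none to reproduce. The check is a comparison of texts, followed by the size of the effect.

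**Step 1. The windows side by side.**

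| Place | Start | End |
|---|---|---|
| 8.1 and 12.6, endpoint sentence | intervention | intervention |
| 12.6, evaluation sentence | consent | end of intervention |
| 8.1, AE CRF | consent | not stated |
| 7.7.8 and 10.1.1, AE CRF | first dose | not stated |
| 7.7.8, collection points | screening (filed as baseline) | 7-day call |
| Table 1, AE row | month 1 visit | 7-day follow-up |

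Consent is signed at screening (7.2.1) and agent is supplied at the baseline visit (7.3.1), so the consent-based and dose-based starts differ for every participant.

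**Step 2. Where they collide.**
- *Consent to first dose.* Inside the evaluation sentence of 12.6 and the 8.1 form rule. Outside the endpoint sentence and the 7.7.8 and 10.1.1 form rule. Events found at screening are baseline under 7.7.8. Events arising between screening and first dose have no agreed status.
- *End of intervention to the call.* Collected under 7.6, 7.7.8 and Table 1. Outside both sentences of 12.6. No section says how these events are reported.

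**Step 3. Weight of one participant.** Input: 20 per arm (7.3.1). One participant is 1/20 = 5 percentage points. The exact (Clopper-Pearson) 95% limits for x events in n are the 0.025 quantile of Beta(x, n-x+1) and the 0.975 quantile of Beta(x+1, n-x). The counts below are assumed for illustration.

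| Events without the disputed case | Events with it |
|---|---|
| 0/20 = 0% (0% to 16.8%) | 1/20 = 5% (0.1% to 24.9%) |
| 2/20 = 10% (1.2% to 31.7%) | 3/20 = 15% (3.2% to 37.9%) |

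**Step 4. Length of the omitted post-treatment period.** Inputs: 7 +/- 3 days (7.6), so 4 to 10 days; 90 +/- 7 days of treatment (schema), so 83 to 97 days. Ratios: 4/97 = 4.1% at the shortest, 7/90 = 7.8% as planned, 10/83 = 12.0% at the longest.

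**Step 5. Length of the pre-dose period.** No section gives the interval from consent to first dose, so this share cannot be computed.

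**Step 6. Effect on the arm comparison.** Suppose a pre-dose event of a given type occurs with probability b in both arms, independently of on-treatment events with probabilities p1 and p0. The proportion with at least one event becomes 1 - (1-b)(1-p) in each arm, and the difference between arms becomes (1-b)(p1 - p0). The difference in proportions therefore shrinks by the fraction b, which the documents do not let us estimate. A difference in expected event counts would not change, because the same background is added to both arms.

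**The case against.** The best defence is that the endpoint sentence governs. On that reading pre-dose events are already excluded, and the consent-to-end sentence only says when participants are assessed. Section 7.7.8 supports this by filing screening events as baseline, and leaving out the call fits a literal reading of the endpoint. The reading is reasonable, but it is only one of those available: 12.6 goes on to summarise all toxicity data, 8.1 puts post-consent events on the AE CRF directly beneath the endpoint, and call-collected events still have no place.

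A reader might also infer four stronger claims that the documents do not support:

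- *The safety rate cannot be built from the AE form.* Section 8.1 starts that form at consent, and the opening sentence of 10.1.1 requires AEs to be recorded with no start limit. Section 10.1.2 captures onset and end dates. The data can probably be sorted; the rule for sorting them is missing.
- *Leaving out the call hides late events in the active arm.* The call is made in both arms, and nothing suggests that events after stopping favour one of them.
- *The stopping rule is affected.* Section 11.4 sets a 50% threshold for grade III or greater events but neither refers to 12.6 nor states a window.
- *Up to a quarter of background events would pre-date treatment.* That needs four weeks from consent to dose, 4/(4+12) = 25%. The 28-day allowance in the Table 1 footnotes concerns laboratory results available before screening and does not give that interval.

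**Conclusion.** The point holds as an inconsistency in the rules for a primary endpoint. The AE CRF starts at two different times, the evaluation window in 12.6 does not match the endpoint sentence just before it, and AEs from the 7-day call are collected without a stated analysis role.

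The size is 5 percentage points of incidence per affected participant, assuming 20 per arm and a participant whose only event of that type lies in a disputed period. How many participants would be affected is unknown. The omitted post-treatment period is about 4% to 12% of treatment time, and the pre-dose period cannot be sized. Sample size, power and alpha are untouched. This should be corrected before the safety tables are specified, but it does not threaten the conduct of a 40-participant feasibility pilot.

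**What to change.** Reconcile 7.7.8, 8.1, 10.1.1, 12.6 and the AE row of Table 1 to one collection window and one analysis window.

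- **Collection:** record AEs from signed consent through the 7-day call, with onset date, on one form.
- **Analysis:** tabulate by arm the events with onset or worsening from first dose through the 7-day call.
- **Baseline:** list events between consent and first dose separately and keep them out of the incidence.
- **If the endpoint stays limited to the intervention period:** show events reported at the call as a separate line by arm, so that they are reported without redefining the endpoint.

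The cost is wording in four sections, one row of Table 1 and at most one extra table line. Onset and end dates are already CRF elements under 10.1.2, and the call is already scheduled, so no new visit or data item is needed.
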